10 OUTCOME MEASURES/ENDPOINTS

10.1 Feasibility outcomes (Appendix 1)

Table 9 Feasibility Outcomes

	asibility Outcomes	T		
	people accessed study web site			
Number of	people complete screening			
questions				
Number of	people screened out	If Yes - Reason	Repor	t by demographics
Number of	people consented		Repor	t by demographics
Number of	people randomised		Repor	t by demographics
	ndomisation maintained	Yes		No
Study arms				1
sbLICBT	Number attended group session	Report by demo	graphic	ς
3521051	Number completed baseline	Data completion of each item for each outcome		
	outcome measure	measure	. Or cac	Tricent for each outcome
	Difference in WSAS score	Overall and score per item		
	screening v attended group session	Overall and scor	e per itt	CIII
	Number completed end of	Data completion	of oacl	h item for each outcome
	treatment outcome measures (6	measure	i Oi eaci	ir item for each outcome
	•	illeasure		
	weeks post baseline)	Data completies	of and	h itam far asah sutasas
	Number completed final outcome	-	i or eaci	h item for each outcome
	measures 12-week post baseline	measure	1	
	Number of participants requesting	Report by demo	grapnic	S
	support			
	Number of support episodes			
	requested			1
	Number of each type of support	Face to Face		e-mail
	episode requested			
DTC	Number completed baseline			
	outcome measure			
	Difference in WSAS score	Overall and scor	e per ite	em
	screening v baseline			
	Number completed outcome			
	measures at 6 weeks post baseline			
	Number completed final outcome			
	measures 12-week post baseline			
DTC move	Number attended group session	Report by demo	graphic	S
to				
sbLICBT				
	Number completed baseline	Data completion	of	Number completed
	outcome measure	each item for ea	ch	baseline outcome
		outcome measu	re	measure
	Number completed end of	Data completion	of	Number completed
	treatment outcome measures	each item for ea		end of treatment
		outcome measu	re	outcome measures
	Number completed final outcome	Data completion	of	Number completed
	measures 12-week post baseline	each item for ea		final outcome
		outcome measu		measures 12-week
			-	post baseline
	Number of participants requesting	Report by demo	graphic	•
	support		0. ~Pc	-
		l		

Number of support episodes requested		
Number of each type of support episode requested	Face to Face	e-mail

10.2 Outcome measures (Appendix 2)

Table 10 Outcome measures

Measure	Description	Reliability and Validity
SECONDARY OUTCOMES		
Brief Resiliency Scale (BRS; Smith et al., 2008)	6-item participant rated questionnaire assessing ability to on a 5 point scale for each item with anchors —Strongly Agree and Strongly Disagree. Items 1, 3, and 5 are positively worded, and items 2, 4, and 6 are negatively worded. Scored by reverse coding items 2, 4, 6 and adding responses varying from 1-5 for all six items giving a range from 6-30 with total divided by number of questions answered. Interpretation: Low Resiliency=1-2.99; Medium Resiliency=3-4.30; High Resiliency=>4.31.	Commonly adopted measure of resiliency and has been used to rate resiliency in a large number of populations (e.g. University students; cancer) across many countries (e.g. UK, China, Brazil, Germany). Adequate test-retest reliability (.69) with good internal consistency Internal consistency was good, with Cronbach's α ranging from 0.80-0.91 across four populations varying in age. Within the two University student populations Cronbach's α = 8.84-0.87.
Patient Health Questionnaire-9 (PHQ-9; Kroenke et al., 2001)	9-item participant rated questionnaire assessing frequency of symptoms of depression over the last 2 weeks. 4-point scale for each item, with anchors at 0=not at all, 1 = several days, 2= more than half the days, 3 =nearly every day. Unidimensional scale. Available in English, Spanish, German, and Dutch versions.	Leading measure of depression widely used in clinical trials, clinical practice, and as part of the NHS Quality and Outcomes Framework (QOF) for UK primary care, and Improving Access to Psychological Treatments (IAPT) Minimum Data Set (MDS). Cronbach's α =0.89 in primary care, test-retest reliability (ICC) 0.84 after 48 hours. Validation studies indicate positive correlations with measures of functional status (r=0.73), disability days (r=0.39), and symptom-related difficulty (r=0.55) At cut-off of \geq 10, excellent specificity (0.88) and sensitivity (0.88) with diagnoses of major depression by structured interview, replicated in a UK population (sensitivity 0.80; specificity 0.92).
Generalized Anxiety Disorder-7 (GAD-7; Spitzer et al., 2006)	7-item participant rated questionnaire assesses frequency of symptoms of anxiety over the last 2 weeks. 4 point scale for each item, with anchors at 0=not at all, 1 = several days, 2= more than half the days, 3 =nearly every day. Unidimensional scale. Available in English, Spanish, German, and Dutch versions.	Leading measure of anxiety widely used in clinical trials, clinical practice, and as part of the UK NHS IAPT MDS. Cronbach's α =0.92, test-retest reliability ICC = 0.83. Convergent validity good, r =.72 with Beck Anxiety Inventory, r = 0.74 with Symptom Checklist-90 anxiety scale.

Measure	Description	Reliability and Validity	
Work and Social	5-item participant rated questionnaire assesses impaired	Leading measure of functioning, widely used in clinical practice,	
Adjustment Scale (WSAS;	functioning, rated from 0 not at all impaired to 8 severely	and as part of the UK NHS IAPT MDS. Cronbach's α range from	
Mundt et al., 2002)	impaired, with respect to work/education, home	0.70 to 0.92, test-retest reliability ICC = 0.73. Interactive voice	
	management, social leisure, private leisure, and close	response administration correlated 0.81 to 0.86 with clinician	
	relationships. Unidimensional scale.	interviews.	
Demographics	Date of birth, gender, country of birth; gender identity		
	(M/F/neither/both); sexual orientation, race/ethnicity;		
	birthplace, parents' occupation, educational attainment,		
	topic of study, year of academic study, level of study		
	UG/PG/apprenticeship.		
Educational Achievement	Academic outcomes from students either via self-report or		
	consent to access student records.		

10.3 Timeframe for Administration of Demographic and Outcome Measures

Table 11 Outcome measures timeframe

	Time Period		_	
Outcome Measure	Screening	Baseline (Treatment Start)	6 Weeks Post Baseline (Treatment End)	12 Week Post Baseline
Demographic	x			
Brief Resiliency Scale		X	x	х
PHQ9	x	x	x	x
GAD7	X	X	x	x
WSAS	X	X	x	x
Feasibility Outcomes				x

10.4 Primary endpoint/outcome

The primary endpoint of the trial is at 12 weeks post baseline.

10.5 Secondary endpoints

The secondary endpoint is at 6 weeks post baseline (treatment end).

10.6 Exploratory endpoints

There are no exploratory endpoints.

11 ACCEPTABILITY FOCUS GROUP

11.1 Focus group invitation

At the end of treatment (6 weeks post baseline), participants that have received the sbLICBT resiliency intervention will receive an email inviting them to participate in a focus group either online or face-to-face or a combination of both.

A template invitation email for initial response is as follows:

"Dear ,

Many thanks for engaging with the Bounce Back CBT resiliency intervention.

Now the provision of support for the 6 week intervention has ended we'd like to invite you to take part in a focus group that will include a maximum number of 10 students that have taken part in the study. The focus group will last for a maximum of 45 minutes.

The aim of the focus group is to help us gain an understanding regarding your attitudes towards the intervention exploring what you liked and didn't like and any improvements you feel could be made to the written intervention or support offered.

To help us improve the intervention moving forwards, we'd really appreciate it if you would be happy to take part in the focus group.

If you are happy to participate: Please contact the researcher who will be in touch to find a suitable date and time.

If you do not wish to participate: You are not obliged to do so, however it would help us to understand any reasons why to improve and future study. If you are happy to inform us of any reasons, please indicate these to the researcher.

Best wishes, Researcher Name"

11.2 Acceptability Prompts for Focus Group

A template is provided below of potential questions and answers that the students who received the intervention will be asked in order to gain a better understanding of their experiences and how to improve the intervention.

1	I would really like to know more about your experience of engaging with the intervention.					
2	What did you think about the group session at the start?					
Liked		Not Like	ed	Needed		Improvements
3	What are your tho	ughts re	garding the writte	en resiliency interv	vention?	
Positi	ive features	Negativ	e features	Improvements-I	Design	Improvement-Language
4	What are your thoughts regarding the intervention being available in other formats?					
On-li	On-line computer App Written for online completi				n for online completion	
5	If at all, what forms of support did you request and what was your experience?					
6	6 If used email support:					
Liked	ked Not Liked Style Improvements				Improvements	
7	7 If used face-to-face support:					
Liked	ted Not Liked Style Improvements				Improvements	
8	If support not used, why not?					
						·

12. STATISTICS AND DATA ANALYSIS

Statistical/methodological advice sought and provided by Exeter CTU and their statisticians.

12.1 Sample size calculation

As a feasibility study with embedded pilot RCT there is no sample size calculation. Rather, data will be used to inform a sample size calculation for any subsequent definitive RCT were the data to demonstrate potential effectiveness.

12.2 Planned recruitment rate

Recruitment of 120 participants into the study across two iterations of intervention delivery (Cohort 1=30 SbRI; 30 DLT; Cohort 2=30 SbRI; 30=DLT) will take place over 28 weeks (June 2023 to December 2023) (originally 1/9-22 to 13/3/23 within a single study site (University of Exeter). Recruitment rate within this timeframe represents a feasibility outcome.

12.3 Statistical analysis plan

A detailed statistical analysis plan (SAP) is to be produced; the main points of the statistical analysis are summarised here.

12.4 Summary of baseline data and flow of patients

The analysis and presentation of the trial will be in accordance with CONSORT guidelines (Schulz et al., 2010). Recruitment, intervention uptake, outcome completion rates and attrition will be reported (with 95% Cls) and shown on a flow diagram.

Premature discontinuation of intervention may be instigated by the participant or investigator. Participants may elect to withdraw from the study if they wish to do so at any time and for any reason (including perceived harms or lack of efficacy of intervention). Researchers may also request that trial intervention be discontinued for reasons of participant safety at any time; such requests will be made to and approved by the PI or an appointed deputy where possible.

Participants will be withdrawn from the study entirely if discovered as ineligible at the time of recruitment. As a self-help psychological intervention, we do not anticipate significant iatrogenic effects or side-effects requiring individual discontinuation. Participants who elect to discontinue their allocated intervention will be requested to continue to provide outcome data. If a participant wishes to withdraw from the study entirely (and not provide further follow-up data) we will ask them if they are happy to allow us to retain the data already provided to the trial; if the participant does not consent to retention of data, the data will be destroyed.

12.5 Primary analysis

Outcomes related to study feasibility and intervention acceptability (see Table 9 and Table 10).

12.6 Secondary analyses

12.6.1 12 week post baseline follow-up comparison

Primary (BRS) and secondary (PHQ-9; GAD-7, WSAS) outcomes will be compared at 12 week follow-up using the statistical approach outlined above.

12.6.2 Repeated measures comparison including all timepoints

Secondary outcomes (resilience, anxiety, depression, work and social adjustment) will be taken at baseline, 6 weeks (treatment duration) and 12 weeks post randomisation. Secondary continuous outcomes will be reported descriptively (mean and standard deviation (SD)) and inferential comparisons will be reported between the two conditions (1) *sbLICBT*; (2) *DTC* to explore potential effect sizes and confidence intervals.

12.7 Interim analysis and criteria for the premature termination of the trial

No interim analyses are planned. In order to detect potential harms the study will monitor potential adverse effects. Adverse and serious adverse effects will result in trial discontinuation if there is cumulative evidence that the intervention may cause harm.

12.8 Other statistical considerations

Primary analyses will be performed by a statistician who remains blinded to group allocation with analyses presented as such to the investigators. The results will be discussed and interpreted prior to the unblinding of group allocations.

13. ADVERSE EVENTS

13.1 Participant welfare and safety

There is no known health risk associated with any of the assessments or the sbLICBT self-help intervention. The risk concerning participation in this study is believed to be low. Further, we anticipate that the self-help will reduce vulnerability and the risk for developing poor mental health and improve well-being and resilience. In our experience from previous projects, participants are happy to participate and enjoy the assessment tasks. We will strive to use tasks that the participants experience as motivational and reinforcing whenever possible. This will also ensure a low attrition rate.

Because the trial is enhancing resiliency and prevention of poor mental health, the initial screening process will exclude anyone with history of severe psychiatric disorder and those reporting elevated suicidality. These individuals will be automatically guided towards appropriate information and sources of help. This process means that individuals likely to have significantly increased risk (e.g., for self-harm and suicidality), and/or for whom more intensive psychological and psychiatric treatment is appropriate, will not be included in the study.

Other than the intervention failing to produce an effect, there is nothing in the literature to suggest possible adverse effects of the assessments and interventions for the young people involved. Versions of components within the intervention have been previously used with no detected harmful effect.

As with all psychological interventions, individuals reflect on their difficulties, which can produce temporary increases in distress, but no more than would commonly occur in daily life. Prior work has provided positive feedback on the sbLICBT self-help intervention and indicated enhanced resiliency, with no serious adverse events reported: as such, the intervention within the trial may benefit individual participants. The likeliest outcome for users who do not find the intervention of benefit is their disengagement from it. In addition, all participants receive more intensive monitoring, with processes to identify and direct all relevant participants to potential sources of help.

As part of our policy for addressing risk and prioritising the welfare of participants, participants are provided with links to online support, access to contact the trial team, and automatic signposting to help and guidance if reporting risk (e.g., suicidal thoughts, as indexed in items within outcome measures such as the Patient Health Questionnaire-9, PHQ-9 on the screening or follow-up websites) or levels of symptoms suggesting a need for help within any of the assessments within the cohort study. These messages include general information on the presenting symptom, recommended actions to make themselves safe, and advice to seek medical help, and direct links to relevant national sources of help.

The main indicators of harm will be the completion of questionnaires by the participants at all assessments (baseline, 6 weeks, 12 weeks). Questionnaires will be automatically screened for signs of severe distress (for example, defined as scores above 20 on PHQ-9 for depression or reports of suicidal ideation), with automatic programmed questions following up to ascertain aspects of risk and to automatically provide users with recommended advice and signpost towards help (family doctor, local hospital, relevant charities; e.g., website link to the Samaritans in the UK. Other indicators would be report of worsening symptoms or suicidality in direct contact from participants to the research team. Individuals reporting severe levels of symptoms or meeting diagnostic criteria for depression will be offered guidance to seek appropriate help from their GP/family doctor, occupational health or student well-being service should this seem necessary.

For those who enter the trial and then indicate risk there will be the option to contact a site researcher via e-mail or telephone to seek advice. This advice will include guidance to seek appropriate help from their GP/family doctor, occupational health or student well-being service should this seem necessary. Project researchers will be trained in and provided with a protocol to assess risk and with standard useful responses in these circumstances (see Section 14 on Risk Management). The trial site has a designated senior clinician [clinical psychologist or CBT Therapist] who will be available as a resource to researchers to provide guidance on clinical issues arising from participants either through

standardized measures or contacts initiated by the participant. If the researcher has serious concerns about a participant, where appropriate, after discussion with the clinician, the clinician will contact the participants (by email, telephone) to review the situation, provide guidance and offer to write a referral letter, subject to participant consent. These procedures will be made explicit in all information sheets. Any concerns detected this way will be recorded on a standardised pro forma, a copy which will be sent to the sponsor for the trial. The same process will be activated in response to any concerns raised by participants at other times, either spontaneously or in responses during the assessments. We will record both serious and non-serious adverse events as defined by the National Research Ethics Service (e.g. deaths; self-harm; serious violent incidents, referral to crisis care or admission to psychiatric hospital) within both groups and report them to the Research Ethics Committee to determine whether events are related to the treatments and to take appropriate action.

13.2 Definitions

Standard definitions for adverse events etc are in the table below. Because the current interventions are digital self-help rather than a medicinal product and involve no biological agent, it is not appropriate to define adverse events etc re any untoward medical occurrence – rather as a psychological intervention, appropriate adverse events would include those related to mental state and behaviour:

- i) Serious adverse events (SAEs) including death, suicide attempt, self-harm, serious accident or violent incident, referral to crisis care or admission to psychiatric hospital.
- ii) Adverse Events (AE) may include significant worsening symptoms of anxiety, worsening symptoms of depression, as operationalized by a reliable deterioration of movement from 'mild' to 'severe' or 'moderate' to 'severe' levels of symptoms on GAD7 or PHQ9 AND a change of ≥4 points on GAD7 or ≥6 points on PHQ9 from baseline assessment to 6 weeks assessment or from 6 weeks assessment to 12 weeks assessment, new instance of self-harm, new instance of suicidality.

The following definitions are therefore adapted in light of this – see **Table 12**.

Table 12 Definitions of Events

Term	Definition
Adverse Event (AE)	Standard: Any untoward medical occurrence in a participant to whom a medicinal product has been administered, including occurrences which are not necessarily caused by or related to that product. Adapted: Any deterioration in mental state or behaviour in a participant to whom the intervention has been administered, including occurrences which are not necessarily caused by or related to the intervention.

Adverse Reaction (AR)

Standard: An untoward and unintended response in a participant to an investigational medicinal product which is related to any dose administered to that participant.

The phrase "response to an investigational medicinal product" means that a causal relationship between a trial medication and an AE is at least a reasonable possibility, i.e,. the relationship cannot be ruled out.

All cases judged by either the reporting medically qualified professional or the Sponsor as having a reasonable suspected causal relationship to the trial medication qualify as adverse reactions.

Adapted: An untoward and unintended response in a participant to an intervention which is related to any dose of the intervention administered to that participant.

The phrase "response to an intervention" means that a causal relationship between an intervention and an AE is at least a reasonable possibility, i.e. the relationship cannot be ruled out.

All cases judged by either the reporting appropriately clinically qualified professional or the Sponsor as having a reasonable suspected causal relationship to the intervention qualify as adverse reactions.

Serious Adverse Event (SAE)

Standard: A serious adverse event is any untoward occurrence that:

- results in death
- is life-threatening
- requires inpatient hospitalisation or prolongation of existing hospitalisation
- results in persistent or significant disability/incapacity
- consists of a congenital anomaly or birth defect

Other 'important events' may also be considered serious if they jeopardise the participant or require an intervention to prevent one of the above consequences.

NOTE: The term "life-threatening" in the definition of "serious" refers to an event in which the participant was at risk of death at the time of the event; it does not refer to an event which hypothetically might have caused death if it were more severe.

Serious Adverse Reaction (SAR)

Standard: An adverse event that is both serious and, in the opinion of the reporting Investigator, believed with reasonable probability to be due to one of the trial treatments, based on the information provided.

Suspected Unexpected Serious Adverse Reaction (SUSAR)

Standard: A serious adverse reaction, the nature and severity of which is not consistent with the information about the medicinal product in question set out in the reference safety information:

- in the case of a product with a marketing authorisation, this could be in the summary of product characteristics (SmPC) for that product, so long as it is being used within it's licence. If it is being used off label an assessment of the SmPCs suitability will need to be undertaken.
- in the case of any other investigational medicinal product, in the investigator's brochure (IB) relating to the trial in question

Adapted: A serious adverse reaction, the nature and severity of which is not consistent with the information about the intervention in question set out in the reference safety information

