7. PARTICIPANT INCLUSION/EXCLUSION CRITERIA

Table 8 Inclusion/Exclusion criteria

Inclusion	Exclusion
Aged 16 or over.	AGED 16<
PHQ9=<9; GAD7=<9	PHQ9>9; GAD7>9
Suicide risk: PHQ9; Q9=<1 and R2=No and R3=	Suicide risk: PHQ9; Q9>1 and R2=Yes and/or R3
No	=Yes
Resident in UK	
Student at the University of Exeter	Past history of psychosis, mania,
	substance/alcohol dependence

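### The score-based adverse-event rule in 13.2(ii) is insensitive for a sample screened at 9 or below, uses undefined severity bands, and conflicts with Table 12 and 13.3

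*Protocol*

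**What the plan says.** Section 13.2(ii) opens its list with "Adverse Events (AE) may include significant worsening symptoms of anxiety, worsening symptoms of depression". Two conditions make this operational, and both must be met. The first concerns bands: "movement from 'mild' to 'severe' or 'moderate' to 'severe' levels of symptoms on GAD7 or PHQ9 AND a change of" a set size. The second fixes that size and the first interval: "≥4 points on GAD7 or ≥6 points on PHQ9 from baseline assessment to 6 weeks assessment". A further interval is then allowed, running between the two follow-up visits. The same list adds "new instance of self-harm, new instance of suicidality". No cut-points are given for 'mild', 'moderate' or 'severe' on either scale.

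Four other places bear on the rule:

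- **Entry limit (Section 7):** "PHQ9=<9; GAD7=<9".
- **A numeric mark for severity (13.1):** signs of severe distress are, by way of example, "defined as scores above 20 on PHQ-9 for depression or reports of suicidal ideation". Sections 14.1.2 and 14.5 use the same PHQ-9 mark for logging and signposting. GAD-7 has no equivalent.
- **PHQ-9 cut-off (10.2):** at 10 or more, the outcome table reports "excellent specificity (0.88) and sensitivity (0.88) with diagnoses of major depression by structured interview".
- **Other adverse-event definitions:** the adapted definition in Table 12 counts any worsening of mental state or behaviour after the intervention, with no threshold. Section 13.3 says that depressive or anxious symptoms do not count unless there is suicidal thinking, planning or an attempt. It also promises to monitor serious deterioration, which it does not define.

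**The concern.** The sample is selected to be well. The deterioration most likely to occur is a move from a low or mild score into the moderate range, and the rule leaves that out. If there is a band below 'mild', as the wording suggests, a student who starts there and reaches 'severe' is not listed either.

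Section 13.1 calls the questionnaires the main indicators of harm, and 12.7 would stop the trial on cumulative evidence of harm. The step that turns questionnaire scores into events therefore matters. A low score-based count would say little about whether students got worse, and would be a weak basis for planning harm monitoring in a definitive trial.

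**Working it through.** The protocol gives no expected harm rate, so there is no figure of its own to reproduce.

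**Inputs from the protocol.** Entry at 9 or less on both scales (Section 7). Point changes of 4 (GAD-7) and 6 (PHQ-9), over baseline to 6 weeks or 6 to 12 weeks (13.2). Scale maxima 9 × 3 = 27 and 7 × 3 = 21 (10.2). N = 120 (8.6).

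**Assumptions.** 'Mild' is 5 to 9 and 'moderate' starts at 10. PHQ-9 'severe' is tried at above 20 (the 13.1 mark), 20 or more, and 15 or more. GAD-7 'severe' is 15 or more.

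**Step 1, one example.** PHQ-9 from 8 to 14: 14 − 8 = 6, which meets the change condition, and 14 is above the entry limit. It is not 'severe' for any cut of 15 or more, so it is not a score-based event.

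**Step 2, smallest rise that can count from a score of 9 or less.**

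- PHQ-9, severe above 20: 21 − 9 = 12.
- PHQ-9, severe 20 or more: 20 − 9 = 11.
- PHQ-9, severe 15 or more: 15 − 9 = 6.
- GAD-7, severe 15 or more: 15 − 9 = 6.

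None is below the stated 6 (PHQ-9) or 4 (GAD-7), so under these cuts the point condition never excludes anyone from an eligible starting score. It can do so between 6 and 12 weeks: 16 to 21 passes 20 but is a rise of only 5.

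**Step 3, possible score pairs.** Count pairs that start at 0 to 9, end at 10 or more, and rise by at least the protocol's threshold.

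- PHQ-9: starts 0 to 4 give 5 × 18 = 90; starts 5 to 9 give 17 + 16 + 15 + 14 + 13 = 75; total 165. The rule counts 5 starts × 7 ends (21 to 27) = 35, or 21%. With severe at 20 or more it counts 5 × 8 = 40; at 15 or more, 5 × 13 = 65.
- GAD-7: starts 0 to 6 give 7 × 12 = 84; starts 7 to 9 give 11 + 10 + 9 = 30; total 114. The rule counts 5 × 7 (15 to 21) = 35, or 31%.

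These are shares of possible pairs, not of participants.

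**Step 4, illustration with assumed distributions.** Gamma-shaped scores with mean 6 and SD 4.5, or mean 8 and SD 5.5, before truncation at 9; correlation between visits 0.5 or 0.7; added mean worsening 0 or 2 points. The rule was applied over both of its intervals. The comparator is a rise from baseline of the protocol's size, ending at 10 or more, at either follow-up. Ranges are over the eight scenarios.

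| Scale, assumed 'severe' | Rule, events per 120 | Comparator, per 120 | Comparator cases missed |
|---|---|---|---|
| PHQ-9, above 20 | 0.7–5.5 | 14–49 | 89–95% |
| PHQ-9, 20 or more | 0.8–6.8 | 14–49 | 86–94% |
| PHQ-9, 15 or more | 4.0–19 | 14–49 | 61–72% |
| GAD-7, 15 or more | 4.3–20 | 18–57 | 64–76% |

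**Step 5, the three definitions side by side.** Take two students who have had the intervention and report no suicidal thinking, with 'severe' read as above 20.

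| PHQ-9 change | 13.2(ii) | Table 12 | 13.3 |
|---|---|---|---|
| 8 to 14 | no | yes | no |
| 8 to 22 | yes (rise 14) | yes | no |

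No two of the three texts agree on both students.

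**The case against.** A reader might infer that the trial's harm count will be near zero by construction. The documents do not support that, for four reasons.

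- **The score rule is only part of the harm data.** New self-harm, new suicidality and serious adverse events also count, and the 13.2(ii) list is introduced as non-exclusive. PHQ-9 alerts are logged under 14.1.2, and 12.6.2 reports the scales by arm. Section 12.7 does not tie its cumulative evidence to this rule.
- **The number of events is not fixed by the text.** It depends on undefined bands and unstated distributions. It is low for PHQ-9 if 'severe' is above 20, but the GAD-7 illustration gives 4.3 to 20 per 120.
- **Reading 'severe' as above 20 is an inference.** Section 13.1 offers that mark as an example for signposting, not as the band in 13.2.
- **The limit of 9 applies at screening.** Both scales are repeated at baseline (10.3), and a saved assessment can be resumed within two weeks (8.3). A baseline above 9 is therefore possible.

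All four points stand and limit the claim to the score-based rule. They do not rescue it. Mild-to-moderate moves are omitted under every band definition, and arm means do not show how many individuals deteriorated. Table 12 would count those moves, but 13.3 would not, so the wider definition cannot be relied on.

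**Conclusion.** The concern holds as a statement about the score-based rule: it is insensitive for this sample, its bands are undefined, and it contradicts two other definitions in Section 13.

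Omission of the 8 to 14 case needs only a 'severe' cut of 15 or more. The 12-point minimum needs 'severe' to mean above 20. The pair counts also need 'mild' to start at 5. The percentages missed rest on assumed distributions and show direction only, though the rule missed more than 60% of the comparator deteriorations in every scenario tried. No expected event count can be taken from the protocol, and a near-zero total is not established. This should be corrected because the questionnaires are the stated main source of harm information.

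**What to change.** 1. Reconcile 13.2(ii), Table 12 and 13.3 into one adverse-event definition. The choice is for the investigators. Changing 13.2(ii) alone would not work, because 13.3 would still exclude symptom-only events.
2. State the band cut-points for both scales in 13.2, and make the score rule apply whatever the starting band.
3. Separately from the event definition, tabulate by arm, for each of the rule's two intervals, everyone who meets the protocol's own change thresholds (4 or more on GAD-7, 6 or more on PHQ-9). Show as subsets those who also move above the entry limit of 9 and those who reach 'severe'.

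The cost is a few sentences and one table; all the scores are already collected (10.3). More non-serious deteriorations would be logged, possibly more than a few per arm. With no added worsening, the illustration still gives 13.5 to 32.5 PHQ-9 rises per 120 ending at 10 or more. These come from ordinary fluctuation and regression to the mean after selection on low scores. The comparison between arms allows for this, most cleanly at 6 weeks, because 9.2 gives the control arm the intervention after that.
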